Aim 1. To assess whether participants in the psychoeducational intervention improved their attitudes condoning dating violence [IPVAS – R] (a manipulation check), we examined mean differences using a paired t-test with covariates in Mplus (Muthén & Muthén, 2007). This technique also allows us to use the FIML estimator within Mplus and to intercorrelate covariates (e.g., anxiety and depression). Please note this analysis only included participants who were assigned to the psychoeducational intervention (and did not include those in the MBST intervention). Please note that a *decrease* in means indicates improvement, as higher scores on the IPVAS – R indicate attitudes that *condone* dating violence.

Aim 2. To assess whether participants in the MBST intervention improved their mindfulness skills (a manipulation check), we examined mean differences paired t-test with covariates. These tests compared the means of mindfulness skills at baseline to the mean of mindfulness skills at follow-up, controlling for covariates identified in preliminary analyses. Please note this analysis only included participants who were assigned to the MBST intervention

³ One potential concern with this analysis plan is that covariates depend on the outcome of interest, so differences in results may be due to differences in covariates included. To address this, we ran analyses with and without the unique covariates; findings remained the same.

(and did not include those in the psychoeducational intervention). Tests were run individually for all four subscales [observing (KIMS – OB), describing (KIMS – DE), acting with awareness (KIMS – AW), acceptance without judgement (KIMS – AC)].

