Aim 3. To assess whether participants in the MBST intervention improved their emotion regulation (a manipulation check), we examined mean differences using paired t-tests with covariates. These tests compared the means of emotion regulation subscales at baseline to the mean of emotion regulation subscales at follow-up, controlling for covariates identified in preliminary analyses. Please note this analysis only included participants who were assigned to the MBST intervention (and did not include those in the psychoeducational intervention). Tests were run individually for all six subscales (lack of emotional awareness [DER – EA], lack of emotional clarity [DER – EC], nonacceptance of emotional responses [DER – NE], impulse control difficulties [DER – IC], limited access to emotion regulation strategies [DER – ER], and difficulties engaging in goal-directed behavior [DER – DE]). Please note that a *decrease* in means indicates improvement, as higher scores on the Difficulties in Emotion Regulation Scale indicate more problems with emotion regulation.

Aim 4a. To assess whether participants in the psychoeducational intervention reduced dating violence perpetration from baseline (before the intervention) to follow-up (after the intervention) we examined paired t-tests with covariates. These tests compared the mean of dating violence perpetration at baseline to the mean of dating violence perpetration at follow-up, controlling for covariates identified in preliminary analyses. Please note this analysis only included participants who were assigned to the psychoeducational intervention (and did not include those in the MBST intervention). Please also note analyses were run separately for each type of dating violence (physical, sexual, psychological).

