Aim 4b. To assess whether participants in the MBST intervention reduced psychological dating violence perpetration from baseline (before the intervention) to follow-up (after the intervention) we examined mean differences using paired t-tests with covariates. These tests compared the mean of dating violence perpetration at baseline to the mean of dating violence perpetration at follow-up, controlling for covariates identified in preliminary analyses. Please note this analysis only included participants who were assigned to the MBST intervention (and did not include those in the psychoeducational intervention). Please also note analyses were run separately for each type of dating violence (physical, sexual, psychological).

Aim 4c. We used a regression framework to investigate the effectiveness of the MBST intervention at reducing dating violence perpetration as compared to the psychoeducational intervention. We chose to run my analyses within a regression framework in Mplus as this allowed for intercorrelations among predictors (e.g., anxiety and depression were included as covariates so we could account for their intercorrelation) and the use of FIML to handle missing data. We used dummy coding to create a variable to differentiate treatment groups. Within a regression framework, we used this dummy-coded variable to predict our outcome (dating violence). We controlled for baseline levels of dating violence perpetration and included other covariates based on preliminary analyses. This analysis, as compared to the analyses for Aims 1 – 3, included participants from both groups. Please also note analyses were run separately for each type of dating violence (physical, sexual, psychological).

Intent to treat analyses. As guided by the Consolidated Standards of Reporting Trials (CONSORT; Schulz, Altman, & Moher, 2010), the number of participants in each group were analyzed according to the intent-to-treat (ITT) principle. ITT is a collective strategy for design, conduct, and analysis in which all participants who are randomized to a group are treated as if

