other group. The co-PI then gave the list back to the lab coordinator who paired the fake participant IDs with the real participant IDs. The lab coordinator then randomly assigned each group to a condition. This procedure was repeated for each semester. The co-PI did not see any real participant IDs until all data collection was completed and the co-PI did not know which participant IDs or numbers corresponded to which treatment group until all analyses were finished.

Blinding. While randomization is one important step in minimizing bias, randomization alone does not solve all issues of bias. Another important factor to consider is blinding, which refers to “the concealment of group allocation from one or more individuals involved in a...randomized controlled trial.” (Karanikolas, Farrokhyar, & Bhandari, 2010, p. 345) If a member of the research team (who is also aware of the hypotheses) knows which participants are assigned to which groups, it can lead to bias throughout the process. For example, a researcher may treat an individual in one treatment group (in this case, the MBST intervention) differently as compared to a participant in another group (the psychoeducational intervention) and this might influence the participants to behave in a way that is in line with the researcher’s hypotheses during assessments. Bias can also be introduced later on in the research process during data analysis. If a researcher knows which group is hypothesized to perform better, the researcher may selectively report results of statistical tests. Therefore, it is critical to blind the researchers throughout as much of the process as possible.

To reduce bias, a few steps were taken (some of which were already mentioned above). First, the co-principal investigator did not see any participant names/emails throughout the data collection process. All participants completed assessments online using their email addresses. A separate researcher (lab coordinator) downloaded the data and assigned participant IDs to the

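### Do the single-arm tests of Aims 1–3 contradict the statement that the co-PI stayed masked until every analysis was finished?

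*Combined protocol and SAP*

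**What the plan says.** Under Randomization, the plan states that "the co-PI did not know which participant IDs or numbers corresponded to which treatment group until all analyses were finished". The Blinding section repeats that condition values were withheld from the co-PI until data collection and analysis were complete. It then adds a sentence about analyses that use the dummy-coded variable, for which she did not know which number stood for which arm.

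The Analysis Plan ties Aims 1–3 to named arms:

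- **Aim 1** (attitudes, IPVAS-R): "Please note this analysis only included participants who were assigned to the psychoeducational intervention (and did not include those in the MBST intervention").
- **Aim 2** (mindfulness, KIMS): MBST arm only; "Tests were run individually for all four subscales".
- **Aim 3** (emotion regulation, DERS): "Please note this analysis only included participants who were assigned to the MBST intervention (and did not include those in the psychoeducational intervention"). Here too each subscale has its own test: "Tests were run individually for all six subscales".

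Aim 4c is set apart: "This analysis, as compared to the analyses for Aims 1 – 3, included participants from both groups". It is also the one aim for which a group variable is described: "We used dummy coding to create a variable to differentiate treatment groups".

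**The concern.** In a two-arm trial, knowing which code belongs in one single-arm test identifies both arms. An analyst told to run the IPVAS-R test in the psychoeducational group, and the KIMS and DERS tests in the MBST group, seems to need the key. Handing over a pre-cut data file does not help, because the scale to be analysed gives the arm away. The only masking device described for the analysis stage is the hidden dummy code, and that belongs to Aim 4c.

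The Blinding section treats masking of the researchers as essential and names selective reporting as the danger. If the codes had been used for Aims 1–3 before Aim 4 was run, masking of the main comparison would have gone too. A reader could then be crediting the trial with a safeguard that it had only in part.

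**Working it through.** The plan gives no total number of tests and no figure to reproduce. The check is a count from the Analysis Plan, followed by the question of whether each block can be run by someone who sees only codes A and B.

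| Aim | Data used | Tests | Can it be run under codes? |
|---|---|---|---|
| 1 | Psychoeducational arm | 1 (IPVAS-R total) | Yes, if run in both A and B |
| 2 | MBST arm | 4 (KIMS subscales) | Yes, if run in both A and B |
| 3 | MBST arm | 6 (DERS subscales) | Yes, if run in both A and B |
| 4a | Psychoeducational arm | 3 | Yes: 4b runs the same tests in the other arm |
| 4b | MBST arm | 3 | Yes: 4a runs the same tests in the other arm |
| 4c | Both arms | 3 | Yes: hidden dummy code |

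**Step 1: size of the apparent conflict.** Aims 1–3 give 1 + 4 + 6 = 11 tests with no planned counterpart in the other arm. Aim 4 gives 3 + 3 + 3 = 9. The total is 11 + 9 = 20, of which 11 + 3 + 3 = 17 use one arm only.

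The count for Aim 4b rests on its closing sentence and on the Aims and Hypotheses section, which list three types of violence. Its opening sentence names psychological violence alone. Read that way, Aim 4 would have 3 + 1 + 3 = 7 tests and the total would be 18. The 11 would not change.

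**Step 2: does a single-arm test require the key?** No. The analyst fits the same 11 models in group A and in group B, closes the results, and after unmasking reports the group that the plan names. Each reported analysis still contains one arm only, as Aims 1–3 require. The cost is 11 extra model runs, or 11 × 2 = 22 if both covariate versions in footnote 3 are repeated. All 20 tests can therefore be run under codes.

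**Step 3: the preliminary analyses.** The dropout comparison and the covariate screen are written without reference to arm, and the baseline comparison between arms can use coded groups. None of them needs the key.

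**Step 4: would knowledge of the arm change a number?** Each Aim 1–3 model is fitted within one arm, so its estimate is the same whether or not the analyst knows the arm's name. Knowledge could act only through discretion over what to run or report, and little is left: all subscales are named, the direction of each hypothesis is stated, covariates enter by association with dropout or with the outcome (p < .05 for the outcome), and footnote 3 reports that findings were the same with and without the unique covariates. Outcomes are self-reported online, so no rater is involved.

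**The case for a change.** The strongest case for a change is literal. Two masking statements, one under Randomization and one under Blinding, carry no qualification. Nothing in the plan describes mirrored runs, a second analyst, or an order in which Aim 4 was closed first. First-person wording in the preliminary analyses and in Aim 4c suggests that one author ran everything. The Blinding section does admit incomplete masking, but that admission concerns the co-PI's part in the sessions and not the analysis. Order matters too, because the hypotheses differ by arm: a significant reduction in violence is expected with MBST (Aim 4b) and a non-significant one with psychoeducation (Aim 4a).

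What stands is that the document does not say how Aims 1–3 were run relative to unmasking. The rest does not follow:

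- Silence on procedure does not show that the masking statements are false, since a simple procedure satisfies both sets of passages.
- Who ran Aims 1–3 is an inference. The masking statements concern the co-PI only.
- The later Blinding sentence refers back to the Randomization statement in terms of dummy-coded analyses, so a narrower meaning is plausible, although the literal wording is broad.
- The selective-reporting worry in that section is about knowing which group is expected to do better. Aims 1–3 compare no groups. The section's first answer to that worry is that analyses were fixed in advance, which holds with or without codes.

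**Conclusion.** No change to the plan. Eleven of the 20 planned tests have no described masking procedure, but all 20 can be carried out under codes, so the masking statements and the single-arm analyses are compatible. The gap is one of reporting, of a kind that analysts fill sensibly. Filling it alters no estimate, test, sample size or conclusion.

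Nor would an amendment gain anything for this trial. The document describes completed work, and re-running models cannot restore masking for anyone who has already seen the codes. A sentence in the trial report on when Aims 1–3 were run relative to unmasking would be a courtesy to readers. The masking statement would need narrowing only if those tests were in fact run with the arm known.

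This conclusion assumes that the analyses were fixed in advance, as the Blinding section says, and that footnote 3's report of unchanged findings is accurate. It does not assume that masking was kept for Aims 1–3. The documents neither establish that nor show that it was broken.
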